Common medications used alone or in combination with corticosteroids are H1 antihistamines. Until recently this was limited to intravenous diphenhydramine. While intravenous diphenhydramine is effective, it carries with it significant adverse effects. Diphenhydramine readily crosses the blood brain barrier producing both H1 receptor-mediated and cholinergic receptor-mediated effects in the CNS. These CNS effects become more frequent and severe in older patients.

A recently published work found that diphenhydramine was effective in relieving urticarial symptoms but produced subjective "sedation".² Sedation is a depressed state of CNS activity, generally considered a decrease in alertness. However, the effects of diphenhydramine go beyond sedation. There is sufficient published data to suggest that diphenhydramine can have negative effects on several specific domains of cognition including reaction time, recognition and recall, working memory processing speed and ability to perform divided attention tasks. These are many of the same domains of cognition involved in skills related to driving an automobile, etc.³⁻⁷

We propose this study to specifically explore the effects of intravenous diphenhydramine on specific domains of cognition. We propose a formal pharmacokinetic/pharmacodynamic (PK/PD) analysis so that models can be developed that allow estimates of these effects when variables such as dose are varied.

SECTION 4.0: OUTCOME MEASURES

The primary outcome will be the difference in the results of the battery of cognitive function tests (Appendix A) after diphenhydramine administration compared to baseline.

The secondary outcomes will be:

1. The difference in the results of the battery of cognitive function tests in elderly subjects (Group B) vs. adult subjects (Group A)
2. The difference in diphenhydramine area under the curve (AUC) in elderly subjects (Group B) vs. adult subjects (Group A)
3. The difference in the results of the battery of cognitive function tests (Appendix A) after diphenhydramine administration compared to baseline in elderly subjects (Group B) vs. adult subjects (Group A)

SECTION 5.0: INCLUSION CRITERIA

The following are required for inclusion in this study:

- 1) Medically-stable volunteers of either gender between 35 and 50 years old (Group A) or over the age of 65 (Group B)
- 2) No medication changes anticipated for the duration of the study except as defined in section 9.4

SECTION 6.0: EXCLUSION CRITERIA

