Measurements will be taken pre-treatment, just after infusion (30-60 min post-infusion), half-way (210-240 min post-infusion), and at the end (450-480 min post-infusion) of the experiment. This design was selected to generate a robust set of richly collected psychometric testing data that can be analyzed over the full-time course of the experiment. In addition, the population PK/PD analysis method to be implemented (see below) will permit a “sharing” of information between subjects. This strategy will permit robust sampling of the psychological effects of each drug after a single dose, and relate these effects to the concentration of diphenhydramine.

Section 7.4: Pharmacokinetic Sampling Schedule/Design (Study Day 2)

All subjects will have PK samples drawn at the following time points from end of study drug administration:

PK Sample Time (min from end of administration)	Acceptable Range (min)
15	+/- 5
30	+/- 5
60	+/- 5
90	+/- 5
120	+/- 5
180	+/- 10
210	+/- 10
360	+/- 10
420	+/- 10
480	+/- 10

Additionally, a sample will be drawn at time 0 at 0-60 minutes prior to start of drug administration.

At time points where both PK samples are taken and psychometric testing is completed, the PK sample will be taken prior to the start of psychometric testing.

Given the limited population of PK data in the literature for diphenhydramine, a rich sampling scheme will be implemented for each subject. The frequent samples after the end of administration at 15, 30, and 60 min will capture the distributional phase of diphenhydramine. Furthermore, by richly sampling all 32 subjects, this will allow for adequate description of PK fixed effects (clearance, volume of distribution, etc.) and the corresponding inter-individual variabilities on each of those terms.

Section 7.5: Adverse Events (AEs)

Subjects will be under continuous observation at the study site. Both medical and nursing staff will be at the study site for the entire study day. Any subject reporting AEs during the study day will be medically evaluated as appropriate. All AEs and treatments will be recorded in the subject's study file. Serious adverse effects will be reported to the IRB according to IRB reporting policy. Subjects will be given direct phone numbers to report any adverse event after discharge from the study site.

SECTION 8.0: ASSESSMENTS

Section 8.1: Battery of Cognitive Function Tests

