The domains of cognitive function that will be measured will be reaction time, movement time, sustained attention, response latency, working memory, visual memory, short-term memory, and new learning. These domains of cognition will be measured before and serially after study drug administration as outlined in the protocol. The specific neuropsychometric tests that subjects will complete are Reaction Time, Rapid Visual Information Processing, Paired Associates Learning, Spatial Working Memory, and Digit Span (Appendix A). These tests have been developed for use in clinical trials by Cambridge Cognition Inc. to assess cognition as a drug safety measure. They have been shown to be sensitive to cognitive decline by pharmacological interventions, confirming their suitability for use in clinical trials to characterize negative effects on various domains of cognitive function.⁸ A Visual Analog Scale will also be used to assess sedation (Appendix A).

SECTION 9.0: ENROLLMENT AND CRITERIA FOR SUBJECT SELECTION

The study will consist of 32 healthy volunteers of any race or ethnicity. Sixteen subjects will be between the ages of 35 and 50 (Group A) and 16 subjects will be aged 65+ (Group B).

Section 9.1: Sample Size Calculation

The expected magnitude of the effect size for impairment and drowsiness is based on our previous work.(7) Taking into consideration the number of subjects that can be reasonably expected to complete the battery of psychometric exams, 32 subjects can be sampled at each of the given time points. Power was calculated using the pwr package in R (version 4.0.2). Using previously published information on cognitive effects of diphenhydramine, this design will result in a power > 0.8 to detect impairing effects of diphenhydramine, and > 0.9 to detect drowsiness effects from diphenhydramine.(7) For impairment, power was calculated at the type I error level of alpha = 0.05 for four sample groups (0, 30-60, 210-240, and 450-480 min) each with 32 subjects/samples and the previously established effect z-score of 0.45. The exact same procedure was used to calculate the power to observe changes in drowsiness scores, but using the previously observed effect z-score of 0.82.

Section 9.2: Females of Childbearing Potential

Females are considered to be of childbearing potential unless they meet one of the following criteria as documented by the investigator:

1. Post-menopausal for at least 1 year
2. Hysterectomy, bilateral oophorectomy, or salpingectomy

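### Section 10.1 compares post-dose tests with baseline by a one-way ANOVA without a subject term, although the same 32 subjects are tested at all four times; the power in Section 9.1 also cannot be verified, because the scale of its effect size is not stated

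*Combined protocol and SAP*

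**What the plan says.** Section 4.0 sets the primary endpoint: "The primary outcome will be the difference in the results of the battery of cognitive function tests" after the drug compared with baseline. Section 8.1 describes repeated testing: "These domains of cognition will be measured before and serially after study drug administration". The Section 7.3 table gives every subject a time 0 and three later times. Two staggered schedules share the same four windows, so each window holds all 16 + 16 = 32 subjects. Section 9.1 confirms that "32 subjects can be sampled at each of the given time points".

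Section 9.1 then treats the windows as groups: "For impairment, power was calculated at the type I error level of alpha = 0.05 for four sample groups", "each with 32 subjects/samples and the previously established effect z-score of 0.45". From this it concludes that "this design will result in a power > 0.8 to detect impairing effects of diphenhydramine". For drowsiness, "The exact same procedure was used to calculate the power to observe changes in drowsiness scores", with 0.82 in place of 0.45 and a stated power above 0.9. The R package is named. The function, the scale of 0.45 and 0.82, and any within-subject correlation are not.

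In one sentence, Section 10.1 assigns a one-way ANOVA with contrasts both to the comparison of Groups A and B and to the comparison of baseline with the post-dose times. No subject or repeated-measures term is named.

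**The concern.** A one-way ANOVA treats the 4 × 32 = 128 scores as independent. Here they are four scores from each of 32 people. Stable differences between people cancel when a subject is compared with his or her own baseline, but a one-way ANOVA leaves them in the error term. If scores within a person are positively correlated, the standard error of a change from baseline is too large, intervals are too wide, and real impairment is more easily missed. This affects the primary comparison of a 32-subject study that sets out to measure the size and duration of impairment.

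The power statement is the only stated sensitivity for that comparison. A z-score is not a defined effect size for a four-group ANOVA, so a reader cannot tell what change the study can detect.

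**Working it through.** **Inputs.** From Section 9.1: four windows, 32 subjects in each, alpha 0.05, effect sizes 0.45 and 0.82. Assumed: within-subject correlation ρ = 0.3, 0.5 or 0.7, equal between all pairs of times; equal SDs (σ = 1); two-sided contrasts.

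**1. The plan's own figure.** One-way ANOVA power comes from the noncentral F distribution with df 3 and 124 and λ = 4 × 32 × f².
- 0.45 as Cohen's f: λ = 128 × 0.2025 = 25.92, power 0.993. The bound of 0.8 is met. With 0.82 as f, power exceeds 0.999.
- 0.45 as the distance between the highest and lowest of four means, in SDs: f lies between 0.45 × √(1/8) = 0.159 and 0.45/2 = 0.225, so λ = 3.24 to 6.48 and power is 0.29 to 0.54. If all three post-dose means shift equally, f = 0.45 × √3/4 = 0.195 and power is 0.42. The bound is not met. With 0.82 the range is 0.78 to 0.98.
- Power 0.8 needs f = 0.296, which is a span of 0.59 to 0.84 SD.

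**2. The planned contrast on paired data.** For baseline versus one later time, the one-way ANOVA uses a standard error of about √(2/32) = 0.25 whatever ρ is. The true standard error is 0.25 × √(1 − ρ) = 0.209 / 0.177 / 0.137.

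The critical value is t = 1.979 (df 124). A first approximation to the type I error is 2 × [1 − Φ(1.979/√(1 − ρ))] = 0.018 / 0.005 / 0.0003. The table also averages over the sampling variation of the error mean square, using 124 × MSE = (1 + 3ρ)χ²(31) + (1 − ρ)χ²(93). Direct simulation agrees to within about 0.001.

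With a subject term the contrast is a t-test with df 93 and noncentrality (0.45/0.25)/√(1 − ρ) = 2.15 / 2.55 / 3.29.

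| Baseline vs one time | ρ = 0 | ρ = 0.3 | ρ = 0.5 | ρ = 0.7 |
|---|---|---|---|---|
| Type I error, one-way | 0.050 | 0.020 | 0.0066 | 0.0007 |
| Power for 0.45 cross-sectional SD, one-way | 0.431 | 0.419 | 0.406 | 0.386 |
| Power for the same change, with subject term | 0.43 | 0.57 | 0.71 | 0.90 |
| 95% half-width, one-way (SD) | 0.49 | 0.49 | 0.49 | 0.49 |
| 95% half-width, with subject term (SD) | 0.50 | 0.41 | 0.35 | 0.27 |

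A paired t-test (df 31), which does not need equal correlations, gives similar power: 0.55 / 0.69 / 0.89 at ρ = 0.3 / 0.5 / 0.7.

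**3. Does correlation break the stated bound?** If 0.45 is Cohen's f, the one-way F-test on correlated data (100,000 simulated trials per setting) has power 0.998 / 0.999 / above 0.999. It does not.

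**4. What 32 subjects can detect.** For a paired t-test, two-sided 0.05, 80% power needs a mean change of 0.511 SD of change. Multiplied by √(2(1 − ρ)), this is about 0.60 / 0.51 / 0.40 cross-sectional SD. If 0.45 is in SDs of change, power is 0.69.

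**The case against.** **The power claim can be right.** Entering the stated inputs with 0.45 as Cohen's f gives 0.993. The source cited for the effect sizes may settle the scale, and reading 0.45 as a span of means is an assumption made here. All of this stands. A reader might infer that true power is below 0.8, or that the calculation contains an arithmetic error. The documents support neither: one input is undefined.

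**Sections 9.1 and 10.1 agree with each other.** Both treat the four times as groups, so the quoted power does describe the planned kind of test. This also stands. The mismatch is between those two sections and the design in Section 7.3.

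**Section 10.1 may mean an analysis of each subject's change from baseline.** Its sentence is short and speaks of differences. But the same sentence applies one-way ANOVA alike to the between-group and the baseline comparison, and Section 9.1 counts the times as separate sample groups. The text as written does not specify a paired analysis.

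**The error is conservative.** Correct. A reader might expect that ignoring repeated measures inflates false positives. For this comparison, with positive correlation, it does the reverse.

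**The study does not hinge on this test.** Section 9.1 also rests the number 32 on feasibility, no decision rule uses the power, and the population PK/PD model in Section 10.2 is a separate analysis that does not depend on it. This limits the consequence, but it does not supply a subject term for the primary comparison.

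**Conclusion.** The analysis in Section 10.1 is wrong for the design as written, and should be corrected. At assumed correlations of 0.3 to 0.7, the one-way contrast has a type I error between 0.020 and below 0.001 instead of 0.05. For a change of 0.45 cross-sectional SD it gives up between 15 points of power (0.42 against 0.57) and about 50 points (0.39 against 0.90). The direction needs only positive within-subject correlation. The size depends on the assumed correlation, on equal correlation between times, and on reading 0.45 in cross-sectional SDs.

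The power statement in Section 9.1 cannot be verified, because the answer runs from 0.29 to 0.993 with the unstated scale. It is not shown to be wrong, nor does the planned test necessarily fall short of 0.8: under Cohen's f it exceeds 0.99 with or without correlation. Nothing here shows that 32 subjects are too few.

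**What to change.** - **Section 10.1:** for the baseline comparison, replace the one-way ANOVA by a repeated-measures ANOVA or a mixed model with a subject term. Keep the same contrasts and state the assumed covariance between times.
- **Section 9.1:** name the function used and the scale of 0.45 and 0.82. Restate both power figures for the within-subject comparison with the assumed correlation. Alternatively, give the detectable change at 80% power: about 0.51 SD of change per test and time point, two-sided 0.05, without multiplicity adjustment.

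The cost is wording in two sections and one recalculation. Sample size, visits and assessments do not change. The restated power may be less favourable than the present figures.

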PROPOSED STUDY TITLE

The Magnitude and Duration of the Central Nervous System Effects following Intravenous Infusion of Diphenhydramine using Pharmacokinetic and Pharmacodynamic Modeling

PRINCIPAL INVESTIGATOR

[name]

NCT NUMBER

NCT05219604

DOCUMENT DATE

2022-FEB-09

SECTION 1.0: STUDY RATIONALE AND SIGNIFICANCE

This study seeks to explore the magnitude and duration of central nervous system (CNS) effects after intravenous (IV) infusion of diphenhydramine. IV diphenhydramine is an antihistamine commonly used in clinical practice as prophylaxis for infusion-related reactions of monoclonal antibodies. Differences in CNS effects between adults aged 35 to 50 and elderly aged 65+ will be explored. This study aims to construct a pharmacokinetic/pharmacodynamic (PK/PD) model describing the magnitude and time course of CNS effects when variables such as dose, rate of infusion, etc. are adjusted. To the knowledge of the investigators, there are no other studies exploring the CNS effects of diphenhydramine with such a wide variety of cognitive tests and as in-depth PK/PD analysis as the present study.

SECTION 2.0: PURPOSE

Objectives:

- To assess the magnitude and duration of CNS impairment produced by intravenous doses of diphenhydramine 50 mg as measured using objective neuropsychometric endpoints.
- To construct a PK/PD model statistically fitted to the individual serum concentrations and CNS impairment data to produce estimates of PK endpoints including area under the curve (AUC), half-life and total clearance as well as PD endpoints including E_{max} (the maximal effect of a drug) and EC_{50} (blood concentrations for 50% of maximum effect).

The PK/PD model will be used to explore the effects on estimates of maximal effect and time course of CNS effect when variables such as dose, rate of infusion, etc. are adjusted.

SECTION 3.0: BACKGROUND

In recent years, the introduction of monoclonal antibodies has significantly increased the number of chronic conditions treated in infusion suites. The reported overall incidence of hypersensitivity reactions to some monoclonal antibodies can be significant. For example, the overall incidence of hypersensitivity reactions to rituximab is reported to be as high as 77% with the first infusion. Fortunately, prophylactic pre-infusion medications can reduce this to less than 10%.¹

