
The PD endpoints, cognitive test result differences between Groups A and B and between baseline and post-diphenhydramine time points, will be assessed via one-way ANOVA with contrast. The PK endpoint will be assessed via one-way ANOVA with contrast of noncompartmental PK analysis. Patient AUCs will be numerically calculated based on patient-specific parameter estimates (i.e, the empiric Bayesian estimates) and compared between Groups A and B.

Section 10.2: Pharmacokinetic/Pharmacodynamic Modeling Strategy

The population PK modeling approach will be implemented using S-ADAPTM. In order to utilize available information in the literature, priors will be obtained for key PK parameters for diphenhydramine in order to leverage a maximum *a posteriori* estimation method. Previous PK studies will be used to supply prior information of the anticipated PK parameters expected from this study. A full step-wise covariate analysis will be done using log-ratio testing with a pre-defined significance level of alpha < 0.05 for forward selection and alpha < 0.01 for backward elimination. Concentrations below the limit of quantification will be handled using the Beal M3 method.

PK data from both Group A (subjects aged 35-50 years) and Group B (subjects aged ≥ 65 years) will be analyzed simultaneously. Patient age will be explored as a possible covariate on the disposition of diphenhydramine.

Intravenous data generated from this study and absorption data following intramuscular administration from literature data will be used to perform model estimates for intramuscular administration.

Continuous PD biomarkers (cognitive test results) will be handled accordingly, which will entail estimation of maximum effect (Emax) and corresponding blood concentrations for 50% of maximum effect (EC50). Categorical PD biomarkers (cognitive test results) will be handled using a hidden Markov method. This method will provide the probability of a patient being at a certain level given the concentration of the drug in the body. This approach has been used extensively to jointly model PK/PD for psychoactive substances.

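### Section 10.1 tests repeated cognitive scores from the same 32 subjects by one-way ANOVA with no subject term or named response, so error rates and power depend on an unstated reading

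*Combined protocol and SAP*

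**What the plan says.** Section 4.0 sets the comparison: "The primary outcome will be the difference in the results of the battery of cognitive function tests" after dosing against baseline. Secondary outcome 1 compares test results between the age groups, and secondary outcome 3 compares the change from baseline between them. Section 7.3 has every subject tested once before dosing and in three windows afterwards. Section 9.0 gives 32 subjects in all, 16 per age group.

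Section 10.1 assigns these comparisons to a single method: "cognitive test result differences between Groups A and B and between baseline and post-diphenhydramine time points, will be assessed via one-way ANOVA with contrast". It gives no subject effect, covariance structure, contrast definition or response variable.

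Section 9.1 computes power at alpha 0.05 for "four sample groups (0, 30-60, 210-240, and 450-480 min) each with 32 subjects/samples", using "the previously established effect z-score of 0.45" for impairment and 0.82 for drowsiness. It concludes that "this design will result in a power > 0.8 to detect impairing effects of diphenhydramine", and more than 0.9 for drowsiness. It states no within-subject correlation and does not define the z-score.

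**The concern.** The four groups of 32 in Section 9.1 can only be the same 32 people. A one-way layout treats their scores as unrelated. Counting time 0 as one of the groups suggests that raw scores are meant. Between-subject variation then stays in the error term of a comparison that should remove it.

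The direction of the error depends on the contrast. Differences within a subject get too large a standard error, so real effects can be missed. Comparisons between subjects that pool repeated scores get too small a standard error, so false positives rise.

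The first objective is "To assess the magnitude and duration of CNS impairment produced by intravenous doses of diphenhydramine 50 mg". Duration depends partly on the later windows, where effects may be smaller than at the peak (an assumption).

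**Working it through.** **Inputs from the documents:** 32 subjects, 16 per age group; four test times; k = 4 and n = 32; alpha 0.05; effects 0.45 and 0.82. **Assumed, because the documents give neither correlation nor SDs:** ρ = 0.3 / 0.6 / 0.8, equal variances and compound symmetry (except step 7), two-sided tests. Simulated values use at least 40,000 trials per setting.

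1. **Stated power.** For a one-way ANOVA, λ = k·n·f². With 0.45 as Cohen's f, λ = 4 × 32 × 0.45² = 25.92 on 3 and 124 df, giving power 0.993; 0.82 gives more than 0.999. Both claims in Section 9.1 are reproduced. If 0.45 is instead a mean difference d in SDs, f lies between d/√8 = 0.16 and d/2 = 0.225, and power is 0.29 to 0.54. If 0.45 is mean change over SD of change, a paired t-test on 32 subjects has power 0.69 two-sided or 0.80 one-sided.

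2. **Baseline contrast, raw scores.** The one-way SE is √(2/32) = 0.25 SD. The true SE is √(2(1−ρ)/32) = 0.209 / 0.158 / 0.112 SD. The ratio is 1/√(1−ρ) = 1.20 / 1.58 / 2.24. Simulated alpha is about 2% / 0.3% / 0.01%. Secondary outcome 3 in an eight-cell one-way layout gives 1.9% / 0.25% / 0.01%.

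3. **Difference detectable with 80% power.** One-way: 1.98 × 0.25 + 0.84 × true SE = 0.67 / 0.63 / 0.59 SD (0.60 by simulation at ρ = 0.8). With a subject term: (1.99 + 0.84) × true SE = 0.59 / 0.45 / 0.32 SD.

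4. **Power at ρ = 0.3 / 0.6 / 0.8:**

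| True difference | One-way | Subject term |
|---|---|---|
| 0.30 SD | 0.18 / 0.12 / 0.06 | 0.29 / 0.47 / 0.76 |
| 0.45 SD | 0.418 / 0.396 / 0.370 | 0.567 / 0.804 / 0.978 |
| 0.65 SD | 0.77 / 0.83 / 0.90 | 0.87 / 0.98 / 1.00 |
| 0.82 SD | 0.94 / 0.98 / 1.00 | 0.97 / 1.00 / 1.00 |

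 At 0.45 SD the relative loss is 1 − 0.418/0.567 = 26%, 1 − 0.396/0.804 = 51% and 1 − 0.370/0.978 = 62%. If 0.45 is Cohen's f, affected windows differ from baseline by 2f = 0.90, 4f/√3 = 1.04 or √8·f = 1.27 SD, depending on the pattern of means. Power is then 0.97–1.00 against 0.99–1.00, a loss of 0–2%.

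5. **Change scores.** At a single window the baseline contrast is a one-sample test on 32 subjects: valid, with no loss. If changes from three windows are pooled as independent, they correlate at 0.5 through the shared baseline. The variance factor is 1 + 2 × 0.5 = 2, and alpha is 2Φ(−1.96/√2) = 17%.

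6. **Group A versus B pooled over four times.** The variance is understated by 1 + 3ρ = 1.9 / 2.8 / 3.4, and the SE by 1.38 / 1.67 / 1.84. Type I error is 2Φ(−1.96/√(1+3ρ)), about 15% / 24% / 29%, and simulation agrees. A comparison at a single window stays near 5%.

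7. **Unequal variances.** Let one post-dose SD be 2 and the others 1. The true variance factor of the contrast is 1 + 4 − 4ρ = 4.6 at ρ = 0.1 and 3.8 at ρ = 0.3. One-way ANOVA uses 2 × (1 + 4 + 1 + 1)/4 = 3.5. Type I error is about 9% and 6%; at ρ = 0.5 it is back below 5%. A subject-blocked analysis with common variance, equivalent here to a random intercept alone, gives 10–11% in this setting. The paired contrast holds 5%.

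**The case against.** **The large losses sit badly with the plan's own figure.** Of the scales tried, only Cohen's f reproduces the stated power in a four-group ANOVA, and there the loss is 0–2%. This stands. A reader might infer from the 0.45 SD row that the trial loses a quarter to well over half of its power. The documents do not support that: it needs a different scale for 0.45 and an assumed correlation.

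**Moderate effects.** A reader might also infer that effects of about 0.3 to 0.65 SD are missed as planned and recovered by the fix. The figures do not bear this out. At 0.65 SD one-way ANOVA usually succeeds, and at 0.30 SD even the subject-level test falls short of 80%. At ρ = 0.3 the two detectable differences are only 0.59 and 0.67 SD.

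**The wording may be shorthand.** One-way ANOVA could mean repeated-measures ANOVA, and differences could mean change scores. The word independent is not in Section 9.1; it is inferred from the four groups and the absence of a correlation. The cited study may define the z-score. These readings are possible, but the plan must say which applies, because they lead to different error rates.

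**Section 10.2 also addresses time course.** The population PK/PD model carries inter-individual variability, so duration does not rest on window contrasts alone. It is not, however, the test assigned to the primary outcome or to secondary outcomes 1 and 3.

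**Conclusion.** The point holds as a specification fault that should be fixed. On the raw-score reading the named method is wrong for the design; on the single-window change-score reading, only the wording and the power basis need correcting. Confidence is high that the subject term, response and effect scale are missing. It is moderate on the size of the consequence, which rests on assumed correlations and variances.

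A reader might infer that conservative describes the whole analysis, so that every positive finding is safe. That cannot be said. It applies to the raw-score baseline contrast and secondary outcome 3, with positive correlation and similar variances. Secondary outcome 1 would be clearly anti-conservative if the four times were pooled as independent, and the baseline contrast mildly so with a doubled post-dose SD and correlation of 0.1 to 0.3. Nor do the documents show that pooling is intended; Section 10.1 simply does not exclude it.

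**What to change.** **Section 10.1.** Name the response for each cognitive endpoint and replace one-way ANOVA with one of these:

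- paired contrasts of each post-dose window minus baseline; or
- a repeated-measures mixed model with time window, age group and group-by-time, using an unstructured or otherwise heterogeneous covariance rather than a random intercept alone.

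Take secondary outcome 3 from A versus B tests on subject-level change (the group-by-time contrasts). Take secondary outcome 1 from a single-window or subject-mean comparison with the subject as the unit.

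**Section 9.1.** Define the scale of 0.45 and 0.82, and restate power for the within-subject contrast over a range of assumed correlations.

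**Cost.** Revised wording, a recalculated power paragraph and minor programming; no new data. The restated power may be less favourable than the present figure.
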